- a on day one of the very first cycle only
- b ECGs are performed at time points specified in 5.2.7 and 6.2.2.1. In the first and second cycle ECGs are performed in triplicate at the related PK sampling time points. Furthermore triplicate ECGs are performed before and at the end of every subsequent BI 6727 infusion.
- c ECGs are performed at time points specified in 5.2.7 and 6.2.2.4. In the first and second cycle ECGs are performed in triplicate at the related PK sampling time points. Furthermore triplicate ECGs are performed before and at the end of every subsequent BI 6727 infusion.
- d optional, only after separate informed consent
- e pre-infusion, and at minutes 30 (≤ 5), 60 (≤ 10) and 120 (≤ 10) after start of BI 6727 infusion
- f before the first administration of the trial drug and after informed consent and review of in- and exclusion criteria
- g subcutaneous cytarabine is administered twice daily on day one until ten
- h including coagulation parameters (see section 5.2.5)
- i for women with childbearing potential at screening and after every other cycle
- k sampling at the time points as specified in table 1 in section 10.1.2. In cycle 2 only at -0.05 and 1 hour after dose.
- m within 14 days before first treatment. Cytogenetics and molecular genetics (see 5.3.4). Pharmacodynamic analysis, i.e. FACS and cytospins (see 5.6)
- n only in the first cycle on day 2, i.e. 24 hours after the end of the first BI 6727 administration: Pharmacodynamic analysis (see section 5.6)
- p initial response assessment after the first treatment cycle, this analysis may be performed up to 3 days earlier to allow for a timely continuation of the treatment. Pharmacodynamic analysis (FACS and cytospins, see section 5.6) at the end of the first cycle.
Bone marrow aspiration after repeated cycles according to 5.1.1. Additional bone marrow aspiration as necessary for confirmation of haematologic DLT (see section 5.2.3) or progressive disease.

FLOW CHART FOR TREATMENT SCHEDULE B
BI 6727 MONOTHERAPY (ONLY PHASE I PART OF THE TRIAL)

Trial Periods	Screen	Treatment							EoT	FU ^s
Cycle *		! 1								
Visit	Screen	1	2 ^t	3 ^t	4	5 ^t	6 ^t	7 ^{**}		
Days	-14 to -1	1 $\forall 1$	5 $\forall 2$	10 $\forall 2$	15 $\forall 2$	19 $\forall 2$	23 $\forall 2$	28 +3		
Informed consent	x									
Demographics	x									
Medical history	x									
Review of in-/exclusion criteria	x	x ^a								
Document ineligibility for intensive treatment	x									

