- k sampling at the time points as specified in table 2 in section 10.1.2. In cycle 2 only at -0.05 and 1 hour after dose.
- m within 14 days before first treatment. Cytogenetics and molecular genetics (see 5.3.4). Pharmacodynamic analysis, i.e. FACS and cytospins (see 5.6)
- n only in the first cycle at visit 2, i.e. 5±1 days after the end of the first BI 6727 administration: Pharmacodynamic analysis (see section 5.6)
- p initial response assessment after the first treatment cycle, this analysis may be performed up to 3 days earlier to allow for a timely continuation of the treatment. Pharmacodynamic analysis (FACS and cytospins, see section 5.6) at the end of the first cycle.
Bone marrow aspiration after repeated cycles according to 5.1.1. Additional bone marrow aspiration as necessary for confirmation of haematologic DLT (see section 5.2.3) or progressive disease.
- q After approval of Protocol Revision I, physical examination, vital signs, weight, ECOG score, and safety laboratory incl. urine analysis should be done as medically indicated at discretion of the investigator. The results should be recorded in the source data only; documentation in the eCRF is not required.
- r After approval of Protocol Revision I, disease assessments and bone marrow aspirations only have to be performed per local standard of practice to support the decision on further treatment with volasertib. The results should be recorded in the source data only; documentation in the eCRF is not required.
- s After approval of Protocol Revision I, FU is completed 21 days after discontinuation of study drug.
- t After approval of Protocol Revision I, Visits 2, 3, 5, and 6 are optional.

**FLOW CHART FOR TREATMENT SCHEDULE C
CYTARABINE MONOTHERAPY (ONLY PHASE IIA PART OF THE TRIAL)**

Trial Periods	Screen	Treatment							EoT	FU
Cycle *		! 1								
Visit	Screen	1	2	3	4	5	6	7**		
Days	-14 to -1	1 ∀1	5 ∀2	10 ∀2	15	19 ∀2	23	28 +3		
Informed consent	x									
Demographics	x									
Medical history	x									
Review of in-/exclusion criteria	x	x ^a								
Document ineligibility for intensive treatment	x									
12 lead-ECG	x								x	
Blood for pharmacogenetics	x ^d									
Physical examination	x							x	x	
ECOG score, weight	x	x						x	x	x
Height	x									
Vital signs	x	x	x	x	x	x	x	x		
Assignment / Randomisation	x ^f									
Adverse events		x	x	x	x	x	x	x	x	x
Concomitant therapy	x	x	x	x	x	x	x	x		
Administration of cytarabine ^g		x	x	x						
Cytarabine compliance check			x	x	x					

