5.6 BIOMARKER - PHARMACODYNAMIC SAMPLING

5.6.1 Methods and timing of sample collection

For direct analysis of effects of BI 6727 and/or cytarabine on the leukaemia cells, bone marrow aspirate samples (or peripheral blood if no bone marrow can be obtained, e.g. punctio sicca) will be collected at screening (all treatment schedules), at visit 2, i.e. 5 ± 1 days after the end of the first BI 6727 infusion (treatment schedules A and B only), and on day 28 in the first cycle only (all treatment schedules). A total of about 5 mL of bone marrow aspirate from each patient (or 5 mL of peripheral blood if no bone marrow can be obtained) will be required for the pharmacodynamic analysis. The sampling of bone marrow will be performed according to standard procedure and only by experienced persons of the respective trial site. Bone marrow aspirate and peripheral blood from samples taken for screening and for response assessment at the end of the first treatment cycle will be used for comparison.

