6.2.2 Treatment phase

6.2.2.1 Visit 1 – day 1

On the treatment days, the following will be obtained and / or performed:

- ! Review of inclusion and exclusion criteria (patient eligibility), in the first cycle only
- ! Body weight and ECOG performance score
- ! Vital signs at time points specified in the flow charts
- ! Adverse events (AEs)
- ! Changes in concomitant therapies
- ! ECG recording (digital, triplicate) at the following time points in treatment schedule A and B only (ECGs in cycle 1 are performed precisely at the related PK sampling time points)
 - prior to start of infusion of BI 6727 (every treatment cycle)
 - immediately before the end of infusion of BI 6727 (every treatment cycle)
 - 2 hours after the start of infusion (= 1 hour after end of BI 6727 infusion)
(1st treatment cycle only)
 - 4 -6 hours after the start of infusion (= 3-5 hours after end of BI 6727 infusion)
(1st treatment cycle only)
 - 24 hours after the start of the infusion (= 23 hours after end of BI 6727 infusion)
(1st treatment cycle only)
- ! Administration of BI 6727 after final confirmation of dose tier (schedules A and B)
- ! Administration of cytarabine (schedules A and C)

- ! Safety lab parameters before trial drug administration as specified in the flow charts and section 5.2.5
- ! Pharmacokinetic blood samples according to Tables 10.1.2: 1 - 10.2.1: 3 (Appendix 10.1)
The date and time of blood sampling must be recorded in the eCRF.
- ! Disease assessment (clinical and in the blood)
- ! Bone marrow aspiration for pharmacodynamic analyses in treatment schedules A and B (FACS and cytospins see section 5.6) 24 hours after administration of BI 6727.
Pharmacodynamic bone marrow sampling only in the first cycle!

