6.2.2.2 Visit 2 – day 5±1

At visit 2 the following will be obtained and / or performed:

- ! Vital signs
- ! Adverse events
- ! Changes in concomitant therapy
- ! Administration of cytarabine (schedules A and C)
- ! Compliance check for and documentation of cytarabine administration on the scheduled previous days
- ! Safety lab as specified in the flow charts and section 5.2.5
- ! Pharmacokinetic blood samples according to Tables 10.1.2: 1 - 10.1.2: 2 (Appendix 10.1) (only schedules A and B). The date and time of blood sampling must be recorded in the eCRF.
- ! Disease assessment (clinical and in the blood)

After approval of Protocol Revision I, visit 2 is optional.

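### The protocol gives two non-overlapping times for the single early pharmacodynamic marrow sample in cycle 1

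*Protocol*

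**What the plan says.** Drug effect on leukaemia cells is secondary endpoint 5 (Protocol 2.3). Five places in the protocol bear on the early on-treatment marrow sample for it:

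- Flow chart for schedule A, footnote n: "only in the first cycle on day 2, i.e. 24 hours after the end of the first BI 6727 administration".
- Section 6.2.2.1 (visit 1): marrow for "pharmacodynamic analyses in treatment schedules A and B (FACS and cytospins see section 5.6) 24 hours after administration of BI 6727".
- Flow chart for schedule B, footnote n: "only in the first cycle at visit 2, i.e. 5±1 days after the end of the first BI 6727 administration".
- Section 5.6.1: "at visit 2, i.e. 5 ± 1 days after the end of the first BI 6727 infusion (treatment schedules A and B only".
- Section 6.2.2.2, headed "6.2.2.2 Visit 2 – day 5±1": the procedure list contains no marrow aspiration.

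Section 5.6.1 names three sampling occasions in all: screening, this early sample, and day 28 of cycle 1. SAP 7.5 says that pharmacodynamics will be analysed separately, outside the clinical trial report.

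**The concern.** A site treating a schedule A or schedule B patient cannot satisfy all of these instructions with one aspiration. Cross-reference does not help: both 24-hour passages send the reader to section 5.6, which gives the other time.

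The synopsis describes the readout as including flow cytometry for cell cycle arrest, so time since dosing is part of what is measured. In schedule A, cytarabine is given every 12 hours on days 1 to 10, so a later sample also follows more cytarabine. If some early samples were taken at about one day and others at about five, treating them as one time point would mix different biological conditions. The procedure is also invasive, which is a further reason for the instruction to be unambiguous.

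**Working it through.** No power, alpha or sample-size figure enters this point. The check sets the passages side by side and does simple time arithmetic.

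**Inputs.** The first infusion is on day 1 and lasts 1 hour (Protocol 4.1). The sampling times are those of the five places quoted above. The position of the marks in the flow-chart grids is not used, because table columns may have shifted in the copy reviewed. The footnotes and sections are complete sentences.

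| Place | Applies to | Stated time | Hours after end of infusion |
|---|---|---|---|
| Flow chart A, footnote n | A | day 2 | 24 |
| Section 6.2.2.1 | A and B | 24 h after administration | 23 to 24 |
| Flow chart B, footnote n | B | visit 2, 5±1 days after end | 96 to 144 |
| Section 5.6.1 | A and B | visit 2, 5±1 days after end | 96 to 144 |
| Section 6.2.2.2 | A and B | no marrow listed | none |

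Section 6.2.2.1 does not say whether its 24 hours run from the start or the end of the infusion. From the start it would be 24 − 1 = 23 hours after the end. The difference is immaterial here.

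**Gap between the two times.** 5 − 1 = 4 days and 4 × 24 = 96 h; 5 + 1 = 6 days and 6 × 24 = 144 h. Against 24 h, the gap is 96 − 24 = 72 h (3 days) to 144 − 24 = 120 h (5 days). The times do not overlap.

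**Is it deliberate schedule-specific timing?** Flow chart A against flow chart B could be read that way. Sections 5.6.1 and 6.2.2.1 rule it out, because each covers both schedules and they disagree. For schedule A, two places say 24 hours and one says 5±1 days. For schedule B, one says 24 hours and two say 5±1 days.

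**A second mismatch within the later time.** Visit 2 at day 5±1 means days 4 to 6. With the infusion on day 1, that is (4 − 1) × 24 = 72 h to (6 − 1) × 24 = 120 h at the same clock time. A window of 5±1 days after the infusion is 96 to 144 h, about days 5 to 7. The two share only about days 5 and 6, although footnote n and section 5.6.1 treat them as the same. On the visit-2 reading, the gap from 24 h would be 48 to 96 h, and there would still be no overlap.

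**The case against.** The contradiction in the text is hard to dispute. The case on the other side concerns what follows from it, and much of that case stands.

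- *A reader might infer that the samples will not be comparable.* That depends on which section each site followed, and the documents do not show this. Only the early sample is in doubt; screening and end-of-cycle sampling are stated consistently.
- *A reader might infer that a comparison of schedules A and B is confounded with time.* No pharmacodynamic comparison of A with B is specified; section 7.3.5.1 plans one for pharmacokinetics only. The schedules are filled sequentially and without randomisation, with B starting at the MTD of A, so such a contrast would not be clean anyway. The randomised contrast is A against C, and C has no early on-treatment marrow sample.
- *A reader might infer that patients have an extra aspiration.* No passage asks for two early samples. Two would arise only if a site tried to obey conflicting sections at once.
- *Little is left to change prospectively.* Section 1.3 says that under Protocol Revision I one ongoing patient stays in the trial. The disputed sample belongs to the first cycle only, and marrow sampling now follows local practice.
- *The pharmacodynamic analysis is not in these documents.* Nothing shows that it pools the two times or ignores actual sampling times.

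None of this removes the contradiction. It limits the consequence to the interpretation of early samples already collected. It also means that A and B need not share one time: different times, stated consistently, would be coherent.

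**Conclusion.** The concern holds as an internal inconsistency in the current protocol text. One early marrow sample has two incompatible times, 72 to 120 hours apart, and the procedure list for the later visit omits it. Early samples for secondary endpoint 5 may therefore differ by 3 to 5 days in time since dosing, within a schedule or between schedules, and may not be comparable.

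This rests on a 1-hour infusion on day 1 and on sites having followed the text as written, in whichever section they used. How many samples fall at each time cannot be told from the documents, and no effect on any pharmacodynamic readout has been shown.

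The point is minor. The MTD, the response analysis, the sample size and the analyses specified in the SAP are untouched. The practical value now lies mainly in handling the existing samples correctly.

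**What to change.** Reconcile footnote n of flow charts A and B with sections 5.6.1, 6.2.2.1 and 6.2.2.2, so that each schedule has one time stated the same way throughout. State whether the clock runs from the start or the end of the infusion, and make the window agree with the visit it is tied to. The documents do not show which time was intended. That choice is for the clinical team, and none is proposed here.

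In the separate pharmacodynamic analysis plan, classify each early sample by its actual time since infusion, report how many fall at each time in each schedule, and do not pool 24-hour with day-5 samples as one time point.

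The cost is a text clarification and one analysis rule. The uncertain part is recovering actual times: section 5.5 requires date and time in the eCRF for pharmacokinetic samples, but section 5.6.1 states no such requirement for the pharmacodynamic marrow. Site or laboratory records may be needed, and samples whose time cannot be established should be reported as such.

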1. INTRODUCTION

1.1 MEDICAL BACKGROUND

Acute myeloid leukaemia (AML) is a heterogeneous clonal disorder of haematopoietic progenitor cells and represents the most common malignant myeloid disorder in adults. AML predominantly affects older adults with median age at diagnosis of about 70 years. Without therapeutic intervention the disease progresses and leads to death within months after initial diagnosis ([R07-2768](#)).

Genetic alterations in leukaemic cells constitute the most important factor for the prognosis of AML ([R07-2768](#), [R07-2770](#), [R07-2774](#)). AML patients are classified in groups of favourable, intermediate, and unfavourable risk. Other factors with impact on prognosis are age, performance score, white blood cell count, blood chemistry disturbances and de-novo versus secondary AML.

Intensive treatment approaches for AML with curative intention include two phases. The first, remission induction treatment, most commonly consists of cytarabine and an anthracycline and is followed by the second phase of post-remission treatment aiming at the consolidation of remission. AML patients under the age of 60 years achieve complete remission (CR) with intensive treatment regimens in up to 75%, while AML patients over 60 years of age (referred to as elderly patients) have a 40 - 60 % chance of CR when receiving intensive remission induction treatment ([R07-2767](#)).

However, while the majority of younger AML patients receives intensive treatment, a substantial number of elderly patients is considered ineligible for this treatment approach ([R07-2773](#), [R07-2854](#)). Therefore the CR rates up to 60% reported in elderly previously untreated AML patients receiving intensive treatment are by no means representative for the entire group of elderly AML patients. For AML patients considered ineligible to receive intensive treatment investigational treatment is widely regarded as the preferred therapeutic option ([R07-2769](#), [R07-2772](#)). For most patients with relapsed AML or AML refractory to induction treatment no satisfactory therapy exists. Currently, major efforts focus on the improvement of the therapy in these subgroups of patients with unfavourable prognosis.

Although patients that are considered as ineligible for intensive treatment constitute a generally accepted subgroup of AML patients, no validated criteria are defined to judge a patient's eligibility for intensive treatment ([R07-2771](#)). The assessment of eligibility for intensive treatment is regularly done for every single patient based on the specialised physician's clinical experience and the comprehensive review of factors like patient age, performance score, organ dysfunctions and co-morbidities, as well as the patient's informed decision.

1.2 DRUG PROFILE

1.2.1 BI 6727

BI 6727 is a highly selective and potent small molecule Polo-like kinase 1 (Plk-1) inhibitor. The pharmacological profile of BI 6727 was evaluated in vitro in enzymatic assays, cellular cytotoxicity assays and assays examining cell cycle progression. In vivo efficacy of BI 6727 was determined in human tumour xenografts in nude mice.

In an enzymatic assay using human recombinant Plk-1 the molecular potency of BI 6727 was in the low nanomolar range. More than 45 kinases tested in parallel with Plk-1 were not inhibited, demonstrating the high molecular specificity of the compound. The compound was also tested for its cellular activity on a panel of tumour cell lines. Cytotoxicity in vitro and inhibition of Plk-1 in enzymatic assays was achieved at comparable concentrations. Activity was not dependent on cellular origin or molecular phenotype. Cell biological profiling revealed that BI 6727 induced a typical Plk-1 mitotic arrest phenotype (G2/M arrest, abnormal mitotic figures) at similar concentrations. When comparing the activity in parental cell lines to the activity in the respective chemo-resistant counterparts activity of BI 6727 was much better conserved than the activity of conventional therapeutics such as taxanes or vincristine.

Efficacy of BI 6727 was shown in various xenograft models. Tumour regression up to complete cures of animals was demonstrated. Tumour regression was also shown in models of larger tumours. Doses shown to be effective were well tolerated and were administered to nude mice 1-2 times per week intravenously.

The non-clinical safety profile of BI 6727 is considered favourable regarding the oncological indication and the antiproliferative principle. In 3-cycle toxicity studies in dogs and rats mechanism-related side effects were observed in organs with high turnover as expected. Main target organs were the gastrointestinal tract (mucosal lesions), bone marrow and lymphatic system. Complete reversibility even of severe lesions at higher doses was observed. Moreover, no evidence for unspecific toxicity affecting other organs such as kidney or liver was found. However, an exploratory investigation on the cardiovascular system in pigs, given at very high doses of up to 30 mg/kg BI 6727, showed that BI 6727 induced QT prolongation starting at a plasma level of 3700 nmol/L and slight QTcSE prolongation in chronically treated dogs starting at 36 mg/m² at plasma levels of about 880 – 1090 nmol/L. The hERG channel was inhibited with an IC₅₀ value of 2.4 µmol/L while the action potential in guinea pig papillary muscle was not affected up to 10 µmol/L. Based on these results, QT-monitoring is continued in the clinical phase II trials with BI 6727. More detailed information is provided in the Investigator's Brochure (IB; [c01694302-14](#)).

To date 50 patients with a variety of tumour types have been treated in a phase I trial with BI 6727. Thirty-one patients were treated at doses at or above 300 mg, with the maximum tolerated dose (MTD) at 400 mg. The results demonstrated that BI 6727 had good tolerability with reversible haematotoxicity (neutropenia, thrombocytopenia) constituting the dose limiting toxicity. No relevant unspecific toxicity has been observed as yet. Encouraging signs of efficacy were seen in two patients with confirmed partial regressions of urothelial and

ovarian tumours, respectively. In addition long term disease stabilizations were observed in several patients. More than 20 courses of treatment were given without signs of persisting or cumulative toxicity.

In the electrocardiogram (ECG) monitoring BI 6727 dose dependant QtcF prolongations at the time of C_{max} have been observed in patients, but no associated clinical events were reported.

By virtue of a different therapeutic principle, new classes of drug substances may be promising either as monotherapy or in combination with already available drugs. In this trial, the safety and efficacy of BI 6727 will be tested in combination with and in comparison to low-dose cytarabine, the most widely established treatment for patients considered ineligible for intensive treatment ([R07-2771](#)); furthermore, in patients with relapsed/refractory AML BI 6727 monotherapy will be investigated.

1.2.2 Cytarabine

Cytarabine (1-beta-D-Arabinofuranosylcytosine) is indicated alone or in combination with other antineoplastic agents for induction of remission and/or maintenance treatment in patients with AML.

Cytarabine (Ara-C) is metabolised *in vivo* to Ara-CTP (arabinoside cytosine triphosphate) phosphorylated compound, which competitively inhibits DNA polymerase and may also inhibit certain acid kinases. Primarily the drug acts as a false nucleoside and competes for enzymes involved in the conversion of cytidine nucleotide to deoxycytidine nucleotide and also incorporation into the DNA. Cytarabine is a cell cycle specific antineoplastic drug and has no effect on non-proliferating cells nor on proliferating cells unless in the S phase.

The major adverse effect of cytarabine is haematological toxicity. Furthermore, gastrointestinal toxicity may also occur. Other reported adverse effects of cytarabine include fever, rash, alopecia, skin ulceration, conjunctivitis, chest pain, urinary retention, dizziness, neuritis, neurotoxicity or neural toxicity and pain, cellulitis and thrombophlebitis (including irritation or sepsis) at the site of injection. Cytarabine has also been associated with renal dysfunction, hepatic dysfunction and jaundice in some patients. It has also been associated with freckling, skin and mucosal bleeding, joint pain. Very rare cases of pericarditis have been reported. Cases of pancreatitis have also been reported.

A cytarabine reaction is characterised by fever, myalgia, bone pain, occasionally chest pain, maculopapular rash, conjunctivitis and malaise. It usually occurs 6-12 hours after administration.

Cytarabine is teratogenic in some animal species. It should not be used in pregnant women. It should not be used in women who may become pregnant, unless a medically acceptable method of contraception is used during the trial. It is not known if cytarabine or its metabolite is distributed into breast milk, therefore it should not be used in breastfeeding women.

For more detailed information please refer to the Summary of Product Characteristics (SPC) provided by the manufacturer.

